1.5 Risks and Benefits

Radiation: Radiation exposure from the studies supported by this grant include the radiation from the dual energy x-ray absorptiometry, and computed tomography scans of the abdomen.

Blood sampling: Blood samples are collected from an indwelling intravenous catheter for this study. Bruising can occur with venipuncture, as can fainting.

Infusion of substrates: We will infuse minute quantities of glucose and palmitate that are labeled with stable isotopes as part of these studies. The quality assurance plans for these compounds are reviewed and approved by the Mayo Clinic Radioactive Drug Research Committee as the designated representative of the FDA. We will also infuse insulin intravenously and give local anesthetics for the tissue biopsies. The insulin is infused using clinical safeguards as well as research pharmacy safeguards under an IND exemption from the Mayo IRB.

Adipose and muscle biopsies: The risks of these procedures include pain, hematomas, bruising, infection, and scarring of the biopsy site.

Insulin infusion: The risk of insulin infusion is hypoglycemia.

Niacin: the risk of niacin infusion is flushing, pruritus, nausea or vomiting.

2 Study Objectives

Primary Objective

To assess the effect of overnight suppression of FFA with intravenous niacin on trafficking of FFA into intramyocellular ceramides and/or DG

Secondary Objective

To assess the effect of overnight suppression of FFA with intravenous niacin on insulin signaling and insulin-stimulated muscle glucose uptake

3 Study Design

This study is a non-randomized, niacin vs. saline control trial of the effects of niacin on intracellular fatty acid trafficking in insulin resistant states. Subjects will be screened at outpatient clinic visit appointments and interested qualified subjects will be consented and offered participation in this trial. Once consent has been obtained baseline values will be established and subjects will begin treatment and follow-up for up to the next 8 weeks.

A final evaluation and collection of lab samples will be conducted at the end of the study.

rebound increase in FFA concentrations. Depending upon the degree of overnight suppression of FFA concentrations, the dose may be adjusted downwards or upwards (maximum rate of 2.8 mg/min) in subsequent studies. At 0400 h an infusion of [$U\text{-}^{13}\text{C}$]palmitate (330 nmol/min) will be initiated to trace FFA contribution to intramyocellular lipids in the euinsulinemic state (13,15). At 0600 h an infusion of [$6\text{-}^2\text{H}_2$]glucose will be started to trace glucose metabolism and continued till the end of the study. Resting energy expenditure will be measured by indirect calorimetry to permit interpretation of FFA flux data. A series of blood samples will be collected between 0830 and 0900 h to measure steady state plasma palmitate and glucose enrichment and concentrations. The volunteers will then undergo a vastus lateralis muscle biopsy as well as abdominal subcutaneous adipose biopsy together for measurement fatty acid metabolites and to provide material for the “pre-clamp” measures of insulin signaling; the niacin infusion will then be discontinued.

Beginning at 0915 h the volunteers will receive a primed, constant infusion of insulin (1 mU/kg/min) together with an infusion of 50% dextrose labeled with [$6\text{-}^2\text{H}_2$]glucose in order to maintain euglycemia. At the start of the insulin clamp the [$U\text{-}^{13}\text{C}$]palmitate will be stopped and [$^2\text{H}_9$]palmitate (400 nmol/min) will be started to measure the contribution of FFA to intramyocellular lipids during hyperinsulinemia (35). At the end of the 5 hour insulin clamp a second muscle biopsy will be collected from the contralateral leg from the first biopsy to avoid the effects of local trauma. This biopsy is taken at 5 h to allow us to measure the accumulation of [$^2\text{H}_9$]palmitate in the intramyocellular lipid metabolites listed above, as well as to detect the loss of [$U\text{-}^{13}\text{C}$]palmitate from the metabolites as a function of their turnover. A series of blood samples for glucose and palmitate enrichment will be collected just prior to each of these biopsies.

The change in the ratio of phosphorylated to total insulin signaling effector proteins between the first and second muscle biopsy will be used to assess the insulin-mediated activation of insulin signaling pathways. We will assess insulin signaling in biopsies taken under basal and insulin stimulated conditions at the level of Akt phosphorylation using capillary Western blot approaches to quantify phosphorylation (80). Glucose disappearance rates under euglycemic, hyperinsulinemic conditions are an excellent reflection of muscle glucose uptake, and this will be

used as our index of muscle glucose disposal. Indirect calorimetry will be done prior to the first and second muscle biopsies to provide context for substrate utilization and energy expenditure. We will perform abdominal subcutaneous adipose tissue biopsies in order to measure fat cell size and the inflammatory characteristics of adipose tissue because these factors have been related to insulin resistance in muscle. The biopsies will be done using sterile technique under local anesthesia and will be done on different sides of the abdomen.

[figure not shown]
3.2 Number of Subjects

Ten upper body obese and 10 Type 2 diabetics (5 male and 5 female in each group) will be recruited to participate in this study to assure we have truly insulin resistant participants in whom improvements in insulin action can be expected.

3.3 Duration of Participation

The duration of participation for each subject would take anywhere between 6 weeks to 3 months, including the 4-8 week interval period, all the visits and overnight stay at the CRTU. The overall recruitment and completion of the study will take about 4 years due to disruptions in scheduling from the COVID pandemic.

Flowchart of Study Events

3.4 Primary Study Endpoints

To determine the contribution of plasma palmitate ($[U-^{13}C]$ and $[^2H_9]palmitate$) to muscle triglycerides, DG and ceramides in saline control and niacin (FFA suppressed) conditions.

3.5 Secondary Study Endpoints

We will also measure the insulin signaling assays and glucose disposal rates, specifically to test the effects of the lower FFA concentrations on insulin signaling and glucose disposal

We will assess whether the incorporation of plasma palmitate into muscle DG is related to changes in the proximal activation by phosphorylation of the insulin signaling pathway during the insulin clamp.

3.6 Primary Safety Endpoints

The only known adverse effects of short term exposure to niacin are skin flushing and pruritus.

We will document the duration and severity of any symptoms during the niacin infusion. (ICH E6, section 6.8)

3.7 Identification of Source Data

The following source data will be directly recorded on the Case Report Form (CRF):

- Patient Reported Outcomes – flushing
- Smoking Status

The following source data will not be directly collected in the Case Report Form (CRF), but will be captured in supportive documentation (study source documents, EMR, study staff maintained excel spreadsheets):

- Laboratory results and clinical interpretation of the values.
- **Blood pressure, temperature, pulse rate. Will be recorded in the EMR by CRTU nursing staff.**
- Height and weight are directly recorded in excel files by study staff.
- Patient Questionnaire (VAS) flushing are recorded in the EMR by CRTU nursing staff.
- CT scan analysis

4 Subject Selection Enrollment and Withdrawal

4.1 Inclusion Criteria

Subjects who meet the following criteria may be included in the study:

1. Males and females between 18 and 65 years of age who are able to comprehend instructions, follow study procedures, willing to sign an informed consent form, and consume an isoenergetic diet eating all meals from Mayo GCRC for at least 3 days prior to study.
2. **Overweight/Obese volunteers** will have a BMI $29.0 - 40.0 \text{ kg/m}^2$
 - **Upper body/visceral obesity (UBO)** in women will be those with a waist-hip ratio (WHR) > 0.85 and/or increased visceral fat by single slice CT scan and/or biochemical evidence of metabolic syndrome as determined by the investigators. Upper body obesity in men will be defined as a waist-hip ratio of > 0.95 and/or increased visceral fat by single slice CT scan and/or biochemical evidence of metabolic syndrome.
3. Volunteers with Type 2 Diabetes will have HbA1C between **6.5 and 11.5%**.
Hold metformin and sulfonylurea for 1 week prior study
Avoid pioglitazone due to long half life

4. Resting vital Signs are within the following range: 95 mmHg < systolic blood pressure < 160 mmHg
45 mmHg < diastolic blood pressure < 100 mmHg
40 bpm < heart rate < 100 bpm
5. Female subjects are eligible if they meet the following criteria:
 - Are not pregnant or nursing
 - All women of childbearing potential will have a negative serum pregnancy test at screening and a negative urine pregnancy test within 48 hours before administering study drug.
 - All women of childbearing potential will use an appropriate contraceptive method including barrier method, oral contraceptive medication, contraceptive device or abstinence while participating in the study.
6. Recent or Current research participation?

If Yes look at consent form and f/u visits:

- Medications that alter fat metabolism possibly given: if yes, exclude
- Weight possible changing in the study
- Amount of blood drawn during the study (if our study plus this one draw \geq 450 ml these should be separated by 8 weeks)

7. Previous labs:

- HbA1C < 6.5% for non-diabetic UBO
- Fasting glucose < 126 mg/dl for non-diabetic UBO
- Hb \geq 11.0 for women and \geq 12 for men
- platelets > 100 000

4.2 Exclusion Criteria

The following will exclude potential subjects from the study:

1. Individuals with a history of a disease process such as:
 - Ischemic heart disease
 - Atherosclerotic valvular disease
 - Blood pressure greater than 160/95 despite antihypertensive medication

2. Smokers > 20 cigarettes per week
3. Concomitant use of medications that can alter serum lipid profile:
 - High dose fish oil (>3g per day),
 - STATINS (if yes hold for 6 weeks and receive PCP's approval),
 - Niacin
 - Fibrates
 - thiazolidinediones
 - Beta-blockers
 - Atypical antipsychotics
4. Allergy to Lidocaine, niacin and/or Niaspan
5. Subjects with any of the following parameters greater than 1.5 times the upper limit of normal:
 - a. Serum creatinine
 - b. Alkaline phosphatase
 - c. Aspartate aminotransferase (AST) unless participant has fatty liver disease, in which case AST can be < 2 times upper limit normal
 - d. Alanine aminotransferase (ALT) unless participant has fatty liver disease, in which case AST can be < 2 times upper limit normal
 - e. Total bilirubin (unless the patient has documented Gilbert's syndrome)

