5.8.4 Return or Destruction of Study Drug

All medications would be given on site. Any patient specific unused medication will be destroyed on site.

6 Study Procedures

Table 1 below lists all of the assessments and indicates with an "x" the visits when they are performed. Subjects should be seen for all visits on the designated day and time.

Subjects who are discontinued before completing the study, and those who withdraw prematurely from the study for any reason, should be scheduled for a visit as soon as possible, at which all of the assessments listed for the "end of Study" visit will be performed. Study visits will occur at Screening, Visit 1 and Visit 2/End of Study.

The maximum duration of the clinical investigation is up to 8 weeks from enrollment (signing of consent, which allows for a 14 day screening period).

Schedule of Events			
	Screening	Inpatient Visit 1	Inpatient Visit 2
Study Day	-14	0	28-56
Written informed consent	X		
History and demographics	X		
Concurrent med reconciliation	X		
Height	X		
Weight	X	X	X
Vitals	X	X	X
Laboratory tests ^a	X*		
Single-slice abdominal CT	X		
DEXA scan	X*		
Adverse event evaluation	X	X	X
Pregnancy test	X ^b	X ^c	
Study Agent (niacin administration)		X	
Insulin and glucose administration		X	X
Isotope administration		X	X
Resting energy expenditure		X	X
Muscle Biopsies		X	X
Adipose biopsies		X	X

a: Complete metabolic panel, CBC w/differential, Lipid Panel, HbA1C, liver function tests if not part of complete metabolic panel

b: Serum pregnancy test (women of childbearing potential) at screening

c: Urine pregnancy test (women of childbearing potential) ≤ 48 hours prior to study drug administration.

*Research DEXA scan, labs, and CT scan completed in the previous 3 months may be used in place of repeating these.

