All adverse events that do not meet any of the criteria for serious, should be regarded as **non-serious adverse events**.

Adverse Event Reporting Period

For this study, the follow-up period is up to 6 weeks from the 1st biopsy visit. Any adverse event occurring during the course of the study period will be reported.

Preexisting Condition

A preexisting condition is one that is present at the start of the study. A preexisting condition should be recorded as an adverse event if the frequency, intensity, or the character of the condition worsens during the study period.

General Physical Examination Findings

At screening, any clinically significant abnormality should be recorded as a preexisting condition. At the end of the study, any new clinically significant findings/abnormalities that meet the definition of an adverse event must also be recorded and documented as an adverse event.

Post-study Adverse Event

All unresolved adverse events should be followed by the sponsor-investigator until the events are resolved, the subject is lost to follow-up, or the adverse event is otherwise explained. At the last scheduled visit, the sponsor-investigator should instruct each subject to report, to the sponsor-

investigator, any subsequent event(s) that the subject, or the subject's personal physician, believes might reasonably be related to participation in this study.

Abnormal Laboratory Values

Research lab results taken between study drug administration and study completion are expected to be abnormal as a result of adipose tissue and muscle biopsies (catecholamines) done during the study. Screening lab values are reviewed by the physician principal investigator in the EMR and documented as reviewed in the EMR. Clinical lab results obtained by a primary care provider or other physician that is not involved in the study in the time that a participant receives the study drug will not be assessed for abnormality.

Hospitalization, Prolonged Hospitalization or Surgery

Any adverse event that results in hospitalization or prolonged hospitalization should be documented and reported as a serious adverse event unless specifically instructed otherwise in this protocol. Any condition responsible for surgery should be documented as an adverse event if the condition meets the criteria for an adverse event.

Neither the condition, hospitalization, prolonged hospitalization, nor surgery are reported as an adverse event in the following circumstances:

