4. For administration of anesthetics, care is taken to administer the minimum amount of lidocaine necessary in order to achieve adequate anesthesia. We are careful to limit the amount administered to much less than that which could cause cardiac arrhythmias.

The most prominent risks to each individual volunteer are pain and bruising related to vascular access and adipose biopsies. These are addressed in the protocol and consent form.

E. SAE Reporting

- SAEs that are unanticipated, serious, and/or possibly related to the study intervention will be reported to the independent monitors for each separate protocol as indicated above, the IRB, the Mayo CTSA Clinical Study and Trials Unit, NIDDK and other oversight organizations as appropriate.
- Anticipated or unrelated SAEs are reported to the IRB, the Mayo CTSA Clinical Study and Trials Unit and NIDDK in accordance with their requirements. As the incidence of pain and bruising with biopsies is 100% none of the oversight organizations or nursing staff has requested this information.

Because these studies do not involve interventions/treatments or follow up laboratory testing, we do not anticipate that abnormal lab values will need to be addressed as they would only be discovered at screening and would make the volunteer ineligible for the study.

V. Data Quality and Safety Review Plan and Monitoring

A. Data Quality and Management

- 1) Description of Plan for Data Quality and Management: The PI will review all data collection forms on an ongoing basis for data completeness and accuracy as well as protocol compliance. A statement reflecting the results of the review will be sent to the NIDDK in the annual report (non-competing continuation). Although there are additional reports to be produced by the study coordinator as a result of this DSMP, there are no substantive changes to the study protocol that might require review by the NIDDK.
- 2) Frequency of Review. The personnel and frequency of data review in these studies varies depending upon the source and type of data. The frequency of data review for this study is summarized in the following table.

Data type	Frequency of review	Reviewer
Subject accrual (adherence to protocol regarding demographics, inclusion/exclusion)	Quarterly	Study coordinator, research fellow and Principal Investigator
Adverse event rates (injuries)	Quarterly	Study coordinator, research fellow, Principal Investigator and Endocrine Research Committee as independent monitor

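### Exclusion item 5d sets its fatty-liver limit on AST instead of ALT, so read literally these participants have no numeric ALT limit

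*Combined protocol and SAP*

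**What the plan says.** Section 4.2, item 5 opens with a general rule: "Subjects with any of the following parameters greater than 1.5 times the upper limit of normal" are excluded. Five parameters follow: creatinine, alkaline phosphatase, AST, ALT and total bilirubin. Three carry an exception: bilirubin for documented Gilbert's syndrome, and the two transaminases for fatty liver disease.

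- Item 5c: "Aspartate aminotransferase (AST) unless participant has fatty liver disease, in which case AST can be < 2 times upper limit normal".
- Item 5d: "Alanine aminotransferase (ALT) unless participant has fatty liver disease, in which case AST can be", followed by the same limit of less than 2 × ULN.

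The two lines differ only in the enzyme named at the start. The exception clause is identical, and in both it refers to AST.

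Three other places bear on how ALT is handled:

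- The schedule of events in section 6 marks laboratory tests at screening only, with the footnote "Research DEXA scan, labs, and CT scan completed in the previous 3 months may be used in place of repeating these".
- Section 8.1 (Abnormal Laboratory Values) states: "Screening lab values are reviewed by the physician principal investigator in the EMR and documented as reviewed in the EMR".
- Section 10.1 (IV.E) says of abnormal laboratory values that "they would only be discovered at screening and would make the volunteer ineligible for the study".

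**The concern.** An exception to a numeric limit should say what replaces it. Item 5c does so. Item 5d lifts the 1.5 × ULN limit on ALT for a participant with fatty liver disease, then restates the AST limit that 5c has just imposed. Read as written, the ALT line sets no ALT limit for that participant.

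Item 5d is the operative criterion and the only numeric ALT rule in the documents. Section 10.1 relies on screening ineligibility to deal with abnormal values, which presupposes that section 4.2 says which values are disqualifying. Section 4.3 requires each criterion to be evaluated and documented, and the annual report described in sections 8 and 8.6 must state whether everyone enrolled satisfied the entry criteria. For a participant with fatty liver disease and a raised ALT, the text and its evident intent can give opposite answers. The exception is also not remote from this population: the sponsor wrote it for a study of upper body obesity and type 2 diabetes.

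**Working it through.** No formula or published figure is involved. The check compares the two items, looks for an ALT limit elsewhere, and applies both wordings to example values.

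**Step 1: the rule for each transaminase, read literally**

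| Item | No fatty liver disease | Fatty liver disease |
|---|---|---|
| 5c (AST) | excluded if AST > 1.5 × ULN | AST must be < 2 × ULN |
| 5d (ALT) as written | excluded if ALT > 1.5 × ULN | AST must be < 2 × ULN; no ALT condition |
| 5d (ALT) with ALT substituted | excluded if ALT > 1.5 × ULN | ALT must be < 2 × ULN |

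As written, the fatty-liver entry for 5d duplicates the one for 5c.

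**Step 2: an ALT limit elsewhere?**

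- Section 4.1 item 7 (laboratory inclusion criteria) covers HbA1c, fasting glucose, haemoglobin and platelets. ALT is not listed.
- Section 6 (schedule of events) and section 6.1 list the tests, ALT among them in 6.1, without limits.
- Section 8.1 provides for physician review but gives no threshold.
- Section 10.1 says that abnormal screening values make a volunteer ineligible but gives no threshold. It cannot mean every value above normal, because section 4.2 allows values up to 1.5 × ULN.

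None supplies the missing number.

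**Step 3: both wordings applied to example values** (multiples of ULN; all other laboratory results normal; values chosen for illustration)

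| Fatty liver | AST | ALT | As written | With ALT substituted |
|---|---|---|---|---|
| No | 1.2 | 1.6 | excluded | excluded |
| Yes | 1.2 | 1.6 | eligible | eligible |
| Yes | 1.2 | 2.5 | **eligible** | **excluded** |
| Yes | 1.9 | 5 | **eligible** | **excluded** |
| Yes | 2.0 | 1.2 | excluded | excluded |

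In the last row 5c alone excludes the participant under either wording. The two wordings disagree only when fatty liver disease is present, AST < 2 × ULN and ALT ≥ 2 × ULN.

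**The case against.** The best case against is that the slip corrects itself. Item 5d is headed ALT and mirrors 5c, and a second AST limit would do nothing, so a sensible reader supplies ALT < 2 × ULN. The study has one site and 20 participants, with a physician principal investigator who reviews the screening results, so there are no other sites to read the line differently. Limits on AST, alkaline phosphatase and bilirubin still apply, and section 4.3.2 requires withdrawal if the investigator judges it to be in the subject's interest. The documents do not tie ALT to a hazard of this infusion: section 1.5 lists flushing, pruritus, nausea and vomiting as the niacin risks, and exposure is on a single occasion. The screening-only laboratory schedule and the 3-month look-back apply to every laboratory criterion and would not change with the correction.

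Most of this stands. The intent is fairly clear, misapplication is not shown to be likely, and the laboratory timing is context, not part of the defect. What does not follow is that the line can be left alone. None of the safeguards gives an ALT number, and an eligibility criterion should not depend on the reader replacing one enzyme with another. The text also does not confirm that 2 × ULN is the intended ALT figure; that is an inference from the parallel with 5c.

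**Conclusion.** The concern holds: item 5d is wrong as written. For participants with fatty liver disease it removes the 1.5 × ULN limit on ALT without setting another, and no other section fills the gap.

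The effect is confined to eligibility and safety screening in the group identified above. Its size among the 20 participants cannot be stated and may be nil. Enrolment of someone with a very high ALT is possible under the text but not shown to be likely. Endpoints, sample size, power and analysis are unaffected.

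The finding that no ALT limit is stated rests on the wording alone. The view that ALT < 2 × ULN was intended rests on the parallel with 5c and needs the sponsor's confirmation. It should be corrected, because an operative eligibility limit is missing and the remedy costs almost nothing.

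**What to change.** In section 4.2 item 5d, change AST to ALT in the exception clause, so that a participant with fatty liver disease must have ALT < 2 × ULN. The sponsor should confirm that this is the intended limit.

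The cost is a one-word change to an eligibility criterion and, at most, a slightly narrower pool of eligible volunteers. Nothing in the statistical plan needs to change.
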